11.5.2 Pharmacodynamic endpoints

Total properdin, total C5 concentrations (% change from baseline) data will be listed by treatment, subject, and visit/sampling time point. Descriptive summary statistics will be provided by treatment and visit/sampling time point.

Summary statistics will include mean (arithmetic and geometric), SD, CV (arithmetic and geometric), median, minimum and maximum.

Novartis

Confidential

Page 84

Amended Protocol Version No. 01 (Clean)

Protocol No. CCLG561X2201A

11.5.3 Immunogenicity endpoints

A positive or negative result will be generated from the immunogenicity assay indicating the presence or lack of presence of anti-CLG561 or anti-LFG316 antibodies. Results from immunogenicity assay will be listed by treatment group, subjects and visit/time. Summary statistics (n, % of subjects with positive/negative results) will be provided by treatment group and visit/time.

11.5.4 Pharmacokinetic endpoints

Total CLG561 and total LFG316 serum concentration data will be listed by treatment, subject, and visit/sampling time point. Descriptive summary statistics will be provided by treatment and visit/sampling time point, including the frequency (n, %) of concentrations below the LLOQ and reported as zero.

Summary statistics will include mean (arithmetic and geometric), SD, CV (arithmetic and geometric), median, minimum and maximum.

Corporate Confidential Information

Novartis

Confidential

Page 85

Amended Protocol Version No. 01 (Clean)

Protocol No. CCLG561X2201A

Corporate Confidential Information

11.5.6 Safety

Adverse events

All information obtained on AEs will be displayed by treatment and subject.

The number and percentage of subjects with AEs will be tabulated by body system and preferred term with a breakdown by treatment. A subject with multiple AEs within a body system is only counted once towards the total of this body system.

Vital signs

All vital signs data will be listed by treatment, subject, and visit and if ranges are available abnormalities (and relevant orthostatic changes) will be flagged. Summary statistics will be provided by treatment and visit.

Clinical laboratory evaluations

All laboratory data will be listed by treatment, subject and visit and if normal ranges are available abnormalities will be flagged. Summary statistics will be provided by treatment and visit.

Novartis

Confidential

Page 86

Amended Protocol Version No. 01 (Clean)

Protocol No. CCLG561X2201A

Ocular assessments

Ocular assessments for safety analyses will include slit lamp examination, dilated fundus examination, best corrected visual acuity and intraocular pressure. All data will be listed by treatment group and subjects. Summary statistics will be provided by treatment group and visit.

For each continuous variable, observed values will be presented descriptively (N, mean, standard deviation, median, minimum and maximum) at each visit by treatment group. Change from Screening (Day -30 to Day -1) will be summarized similarly. Also, categorical summaries depending on the parameter will be presented. These reports will be supported by individual subject listings. Details will be described in the statistical analysis plan.

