2.1 Primary objective(s)

Objective	Endpoint

 To evaluate the safety of 12 (every 28 days) IVT injections of CLG561 as a monotherapy and in combination with LFG316 as compared to sham. 	
 Incidence and characteristics of treatment-emergent AEs. Treatment-emergent changes from baseline through Day 421 in ocular and systemic parameters.

 To evaluate in the study eye the efficacy of 12 (every 28 days) IVT injections of CLG561 as a monotherapy and in combination with LFG316 as compared to sham on the growth of GA lesion size as assessed by FAF based on the change from baseline to Day 337. 	
 Change in GA lesion size from baseline to Day 337 as measured by FAF.

Novartis

Confidential

Page 41

Amended Protocol Version No. 01 (Clean)

Protocol No. CCLG561X2201A

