7.5 Early study termination

The study may be terminated at any time for any reason by Sponsor. Should this be necessary, subjects must be seen as soon as possible and treated as a prematurely withdrawn subject. The Investigator may be informed of additional procedures as requested by the Sponsor in order to ensure that adequate consideration is given to the protection of the subject's interests.

The Investigator is responsible for informing IRBs/IECs of the early termination of the trial. In the case of representation by a central IRB, the Sponsor may be delegated this responsibility.

8 Procedures and assessments

Subjects must be seen for all visits on the designated day, with the assessments performed as per schedule, within the allowed "visit/assessment window", and as specified in the MOP.

A single rescreening is permitted only for patients who failed screening under the original protocol but who would have qualified under the amendment 1 revised selection criteria. In addition to the criteria that were changed, the rescreened patients must fulfill the unchanged selection criteria at both screenings to be eligible. Since the inclusion criterion related to lesion size is now only relevant to a single eye (study eye), for lesion size, the rescreening is limited to eyes which qualified in the original screening. For example if the left eye qualified in the original screening, only the left eye can be rescreened as the study eye. If both eyes had qualified previously on the basis of the lesion size but the eyes had failed on the basis of the visual acuity both eyes are candidates for rescreening.

The subject number previously used will be retained in the database. A new subject number is not required. The original informed consent date is retained in the database. The new informed consent date is captured in the source. A new screening date with data for the assessments is captured in the database.

All data obtained from these assessments must be supported in the subject's source documentation. Source documentation must be available for all data collected during the study. IF it becomes necessary to repeat an evaluation, THEN the results of the repeat evaluation must be recorded in the source documents and the valid measurements and evaluation must be recorded on the eCRF.

All screening, baseline and pre-injection assessments must be completed prior to drug

Novartis

Confidential

Page 59

Amended Protocol Version No. 01 (Clean)

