CCLG561X2201A	Screen	Treatment Period																		EOS ⁶	
		N/A	V1	V2	V3	V4	V5	V6	V7	V8	V9	V10	V11	V12	V13	V14	V15	V16	V17		
Visit Numbers ¹	-30 to -1	BL/D1	D2	D8	D15	D29	D30	D57	D85	D113	D141	D169	D197	D225	D253	D281	D309	D337	D421		
Day	-30 to -1	BL/D1	D2	D8	D15	D29	D30	D57	D85	D113	D141	D169	D197	D225	D253	D281	D309	D337	D421		
CLG561 and LFG316 concentration sample collection		X ³	X	X	X	X ³				X ³			X ³		X ³		X ³	X	X		
Corporate Confidential Information																					
IG sample collection			X ³				X ³			X ³			X ³		X ³		X ³	X	X		
Corporate Confidential Information																					

¹ Visit structure is given for internal programming purposes only

² Body temperature, blood pressure, and pulse rate must be measured prior to IVT injection

³

Corporate Confidential Information

Unscheduled visit assessments as needed and as determined by the investigator

Corporate Confidential Information

Table 8-2 Ocular assessments

CCLG561X2201A	Screen	Treatment Phase																FU	EOS ¹⁰
		N/A	V1	V2	V3	V4	V5	V6	V7	V8	V9	V10	V11	V12	V13	V14	V15	V16	
Visit Number	N/A																		V18 (V777)
Day	-30 to -1	BL / D1	D2	D8	D15	D29	D30	D57	D85	D113	D141	D169	D197	D225	D253	D281	D309	D337	D421
Visit Window (Days)			+/- 1	+/- 1	+/- 1	-2	+ 1	+/- 5	+/- 5	+/- 5	+/- 5	+/- 5	+/- 5	+/- 5	+/- 5	+/- 5	+/- 5	+/- 5	+/- 7
Injection		1				2		3	4	5	6	7	8	9	10	11	12		
Ocular examination ^{1,2,3}																			
Best corrected visual acuity	OU	OU	OU	OU	OU	OU	OU	OU	OU	OU	OU	OU	OU	OU	OU	OU	OU	OU	
Low luminance visual acuity		OU	OU			OU	OU	OU	OU	OU	OU	OU	OU	OU	OU	OU	OU	OU	
Intraocular pressure	OU	OU ⁴	SE	SE	SE	SE ⁴	SE	SE ⁴	SE										
Slit lamp biomicroscopy	OU	OU	SE	SE	SE	SE	SE	SE	SE	SE	SE	SE	SE	SE	SE	SE	SE	OU	
Dilated ophthalmoscopy	OU	OU ⁵	SE	SE	SE	SE ⁵	SE	SE ⁵	SE	OU									

Corporate Confidential Information

Color fundus photo	OU	OU								OU			OU			OU	OU	OU
Fundus autofluorescence	OU	OU								OU			OU			OU	OU	OU
Fluorescein angiography	OU																	OU

Corporate Confidential Information

Novartis
 Amended Protocol Version No. 01 (Clean)

Confidential

Page 64
 Protocol No. CCLG561X2201A

Visit Number	Screen	Treatment Phase															FU	EOS ¹⁰		
		N/A	V1	V2	V3	V4	V5	V6	V7	V8	V9	V10	V11	V12	V13	V14	V15	V16		
Day	-30 to -1	BL / D1	D2	D8	D15	D29	D30	D57	D85	D113	D141	D169	D197	D225	D253	D281	D309	D337	D421	V18 (V777)

Corporate Confidential Information

All ocular examinations may be performed at the physician's discretion

² OU: both eyes

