³ SE: study eye

⁴ For all visits requiring an IVT injection, IOP MUST be measured before and after the injection in the study eye

⁵ For all visits requiring an IVT injection, dilated ophthalmoscopy MUST be performed before the injection and immediately after the injection in the study eye
 Corporate Confidential Information

⁸ To be done at select sites only, see MOP for additional details

⁹ Assessment at screening is for source documentation purposes only

¹⁰ Unscheduled visit assessments as needed and as determined by the investigator, imaging not required

Corporate Confidential Information

Novartis

Confidential

Page 65

Amended Protocol Version No. 01 (Clean)

Protocol No. CCLG561X2201A

Table 8-3 Post-injection exams at injection visits

Visit	BL / V1					All injection visits									
Day	D1														
Injection	Inj 1														
Time point															
		Pre-Injection	Immediately Post-Inj	30 minutes Post-Inj	60 minutes Post-Inj, if required	Q 30 minute interval, if required	Pre-Injection	Immediately Post-Inj	30 minutes Post-Inj	60 minutes Post-Inj, if required					
Gross visual acuity		SE					SE								
IOP	OU	SE	SE	SE ¹	SE ²	SE	SE	SE	SE ¹	SE ²					
Dilated Fundus	OU	SE				OU	SE								
Anterior Chamber Paracentesis, if required ³		SE					SE								

¹ If the pressure is elevated >10 mmHg above pre-injection or above 30 mmHg when measured at 30 minutes post-injection it must be measured again at 60 minutes post-injection.

² If IOP still elevated at 60 min post-injection, repeat at 30 minute intervals until pressure is < 10 mmHg above pre-injection pressure or < 30 mmHg.

³ Perform anterior chamber paracentesis if no retinal perfusion 2 or more minutes after injection.

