- Grade 2 aqueous flare and/or Grade 2 or 3 aqueous cells that fail to decrease to 1 or less within 30 days of the onset of the event (see MOP for grading scale)
- Grade ≥ 2 vitreous haze and/or Grade ≥ 3 vitreous cells (see MOP for grading scale)
- ≥ 30 letter decrease in BCVA compared with Baseline visual acuity
- Sustained (> 15 minutes) loss of light perception due to elevated IOP
- IOP > 30 mmHg at/past 60 minutes post injection
- New retinal tear or detachment
- New vitreous hemorrhage $> 2+$ severity that does not resolve within 30 days of the onset of the event (see MOP for grading scale)

If an ESI occurs in a study subject, a decision will be made by the Sponsor concerning further exposure to study treatment. The study subject will be followed for resolution of the ESI and a decision will be made by the Sponsor concerning further participation in the study.

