11.5 Analysis of secondary and exploratory variables

11.5.1 Efficacy endpoints

Analyses will be performed for both the PP set and the FAS.

Potential treatment effects will primarily be assessed based on the difference in change from baseline in the study eye between active treatment and sham treatment. In addition, the corresponding difference between study and fellow eye will be explored within the active treatment arms.

At time points assessed, each efficacy endpoint will be presented graphically and by descriptive statistics provided for observed absolute values and changes from baseline. Changes from baseline will be compared between treatment arms using ANOVA models and/or stratified/unstratified Cochran-Mantel-Haenszel Tests.

Corporate Confidential Information

For treatment differences and differences between study and fellow eye 80% confidence intervals will be provided.

The following secondary endpoints will be evaluated:

- Change in geographic atrophy lesion size from baseline to Days 85, 169, 253, 337 and 421 as measured by fundus auto-fluorescence
- Change in BCVA, low luminance visual acuity and low luminance visual acuity deficit from baseline by visit up to Day 337 as measured by ETDRS in the overall population and in subsets of patients with baseline visual acuity < 73 letters
- Subject status regarding ≥ 15 letters, ≥ 10 letters, and ≥ 5 letters change from baseline in BCVA by visit up to Day 337
- Average change in BCVA/low luminance visual acuity/low luminance visual acuity deficit from baseline to the period Day 281 to Day 337

For the changes in geographic atrophy lesion size from baseline between either of the active arms and sham as measured by FAF, the same analysis model used for the primary hypothesis (Section 11.4.2) will be used.

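### Section 11.5.6 measures change in BCVA and IOP for safety from Screening, although the primary safety endpoint is change from baseline and a pre-injection Day 1 value is collected

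*Protocol*

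**What the plan says.** The first primary objective in Protocol Section 2.1 is safety against sham. Besides adverse events, its endpoint is "Treatment-emergent changes from baseline through Day 421 in ocular and systemic parameters".

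Section 11.5.6, under its ocular paragraph, lists what is covered: "Ocular assessments for safety analyses will include slit lamp examination, dilated fundus examination, best corrected visual acuity and intraocular pressure". Continuous variables are to be described by visit and arm, and then: "Change from Screening (Day -30 to Day -1) will be summarized similarly". The paragraph adds categorical summaries and listings and leaves details to the SAP.

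Other parts of the protocol use baseline for BCVA. The secondary endpoints in Section 11.5.1 cover BCVA, low luminance acuity and "low luminance visual acuity deficit from baseline by visit up to Day 337 as measured by ETDRS". In Section 9.3, one adverse event of special interest is a loss of 30 letters or more, worded as a "letter decrease in BCVA compared with Baseline visual acuity".

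**The concern.** In this protocol Screening and baseline are different visits, up to 30 days apart. A change that starts at Screening is not the change named in the primary safety endpoint, because it takes in a stretch of time before any treatment was given.

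Three things follow:

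- For IOP at every visit, and for BCVA after Day 337, the visible text specifies no change summary of the continuous variable other than the one from Screening. On those items the protocol does not carry out its own primary safety endpoint.
- The same BCVA reading will appear with one change in the safety tables and another in the efficacy tables and the special-interest rule. A reader who compares them will find that they disagree.
- The mismatch weighs most at the early post-injection visits, where a within-arm change ought to reflect the injection most directly.

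**Working it through.** The plan gives no figure to reproduce. The check is a comparison of the text, followed by simple arithmetic for scale.

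**Is Screening a synonym for baseline here?** No. Table 8-2 has one column for Screening (Day -30 to Day -1) and a separate one for BL / D1. Section 11.5.6 also prints the Screening day range, so loose wording is not a plausible explanation.

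**Does a Day 1 pre-injection value exist?** Yes, for both variables.

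- BCVA: the Table 8-2 row opens with "Best corrected visual acuity OU OU", that is, both eyes at Screening and again at BL / D1. The IOP row opens in the same way.
- Timing: Section 8 states "All screening, baseline and pre-injection assessments must be completed prior to drug" administration.
- IOP: footnote 4 of Table 8-2 adds "For all visits requiring an IVT injection, IOP MUST be measured before and after the injection in the study eye". Table 8-3 also lists a pre-injection IOP on Day 1.

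**Which reference does each part of the protocol use?**

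| Item | Section | Reference | Runs to |
|---|---|---|---|
| Primary safety endpoint, ocular and systemic | 2.1 | Baseline | Day 421 |
| BCVA secondary endpoints | 2.2, 11.5.1 | Baseline | Day 337 |
| BCVA special-interest event | 9.3 | Baseline | no cut-off stated |
| Continuous ocular safety variables | 11.5.6 | Screening | each visit |

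Only Section 11.5.6 departs from baseline.

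**How much of the change interval precedes treatment?** I assume there is no Day 0, since the schedule goes from Day -1 to Day 1. This agrees with Section 3.6, which gives about 451 days in all: 30 + 421 = 451.

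Earliest Screening, Day -30, lies 30 days before Day 1. The interval to Day d is 30 + (d - 1) = 29 + d, so the untreated share is 30 / (29 + d). Latest Screening, Day -1, lies 1 day before Day 1. The interval is then 1 + (d - 1) = d, and the share is 1 / d.

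| Visit | Screening at Day -30 | Screening at Day -1 |
|---|---|---|
| Day 2 | 30/31 = 96.8% | 1/2 = 50.0% |
| Day 8 | 30/37 = 81.1% | 1/8 = 12.5% |
| Day 15 | 30/44 = 68.2% | 1/15 = 6.7% |
| Day 29 | 30/58 = 51.7% | 1/29 = 3.4% |
| Day 337 | 30/366 = 8.2% | 1/337 = 0.3% |
| Day 421 | 30/450 = 6.7% | 1/421 = 0.2% |

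These are shares of elapsed time. They do not say how much BCVA or IOP actually moves between Screening and Day 1, and the protocol gives no figure for that.

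**The case against.** The strongest reply is that Section 11.5.6 is an outline. It names no change summary at all for vital signs or laboratory data, it defers details to the SAP, and it does not say that change from Screening is the only change to be shown. The categorical summaries have no fixed reference. The 30-letter special-interest event is counted against baseline with no Day 337 limit. Observed values are tabulated at each visit, Day 1 included, so mean change from Day 1 could be approximated from the tables and individual changes read from the listings. Acute IOP rises are judged against the same-day pre-injection reading. The visible text does not define baseline, and for laboratory tests Screening is the only scheduled pre-treatment sample, so baseline in Section 2.1 cannot mean Day 1 for every parameter.

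Some of this stands. The SAP could add a baseline-referenced table, no data would be lost, and the laboratory point limits how far any correction should reach. The time shares also do not demonstrate harm.

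The conflict remains, however. The protocol did not leave the reference open: it named one, and that one disagrees with its own endpoint. Event counts and categorical tables are not change-from-baseline summaries of a continuous variable. The laboratory argument does not reach a sentence that sits under ocular assessments, where a Day 1 value is scheduled.

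**Conclusion.** The concern holds. Section 11.5.6 fixes Screening as the reference for change in BCVA and IOP, while Sections 2.1, 2.2, 9.3 and 11.5.1 use baseline and a pre-injection Day 1 reading is scheduled for both.

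The consequence is modest. The summaries are descriptive, the randomised arms share the same reference and so no between-arm bias is expected, and efficacy results and sample size are untouched. What suffers is the match between the primary safety endpoint and its reporting, and the consistency of the BCVA changes in the report. By elapsed time the mismatch can dominate the early visits (up to 97% at Day 2) and is at most 8% at Day 337 and 7% at Day 421.

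This rests on reading BL / D1 as baseline for ocular variables, on there being no Day 0, and on the visible text only. An unseen SAP may already add a baseline-referenced table, but the protocol sentence would still need correcting.

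**What to change.** In Section 11.5.6, replace the Screening reference and its day range with *change from Baseline (Day 1, pre-injection)*, restricted to the continuous ocular variables. Do not extend the change to hematology, chemistry and urinalysis, whose only scheduled pre-treatment sample in Table 8-1 is at Screening.

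The cost is one phrase. No visit, assessment or data item is added, because the Day 1 pre-injection readings are already scheduled.

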11.5.7 Other assessments

Corporate Confidential Information

Novartis

Confidential

Page 87

Amended Protocol Version No. 01 (Clean)

Protocol No. CCLG561X2201A

11.6 Sample size calculation

A sample size of 30 PP evaluable subjects per treatment arm will allow identification of a treatment difference of 0.67 mm^2 in lesion size change from baseline to Day 337 (representing a 33% reduction in lesion growth rate, assuming an average natural disease progression of 2.0 mm^2 per year) at a one-sided alpha level of 0.1 with a power of 80% assuming a standard deviation of 1.2 mm^2 .

In anticipation of a drop-out /protocol deviation rate of 20%, a total sample size of ~114 randomized subjects (~38 subjects /arm) is planned for the current study to ensure sufficient study completers for the above described PP analysis. Depending on ongoing monitoring of the drop-out / protocol deviation rate the need for additional recruitment will be assessed to ensure 90 PP evaluable subjects are available for the Day 337 analysis.

Corporate Confidential Information

12 Ethical considerations

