Data analysis	
Primary Endpoint Change in GA lesion size from baseline to Day 337
 
Hypotheses One-sided hypotheses of superiority of active related to the comparison of each of the two active arms vs control (sham injections). The comparison of the two active arms will be done descriptively.
 
Primary analysis data set The primary efficacy analysis data set is a per-protocol (PP) set. Key PP criteria are compliance with the GA specific inclusion criteria, the monthly injection schedule up to Day 337 (not missing greater than 1 in any 6 months period or not missing 2 consecutive doses) and available baseline and Day 337 and/or Day 253 lesion size assessments. Missing values of lesion size on Day 337 will be imputed based on linear regression/extrapolation.
 
Statistical testing strategy For hypotheses-testing a global one-sided alpha of 0.2 is considered. With the two hypotheses being tested in parallel using the Bonferroni multiplicity adjustment, the nominal one-sided alpha for each single hypothesis will be 0.1.
 
Statistical method The lesion size change from baseline to Day 337 will be analyzed by an ANOVA model including but not limited to the class variable representing categories of baseline lesion size (edge length) and categories of lesion location.
 
Sample size A sample size of 30 per-protocol (PP) evaluable subjects per treatment arm will allow identification of a treatment difference of 0.67 mm² in lesion size change from baseline to Day 337 (representing a 33% reduction in lesion growth rate, assuming an average natural disease progression of 2.0 mm² per year) at a one-sided alpha level of 0.1 with a power of 80% assuming a standard deviation of 1.2 mm². In anticipation of a drop-out /protocol deviation rate of 20%, a total sample size of ~114 randomized subjects (~38 subjects/arm) is planned for the current study to ensure sufficient study completers for the above described PP analysis. Depending on ongoing monitoring of the drop-out/protocol deviation rate the need for additional recruitment will be assessed to ensure 90 PP evaluable subjects are available for the Day 337 analysis.

Key words	Geographic atrophy, GA, macular degeneration, dry AMD, IVT, intravitreal, retinal diseases, FAF

1 Introduction

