3.1 Study design

This study employs a multi-center, randomized, sham-controlled, single-masked design. Approximately 114 eligible subjects (38 in each treatment arm) with GA will be randomized in a 1:1:1 ratio to obtain approximately 90 evaluable subjects completing the study per protocol. Subjects will receive one of three treatment modalities:

1. CLG561 (10 mg/100 µL)
2. CLG561 (5 mg/50 µL) + LFG316 (5 mg/50 µL)
3. Sham injection

The treatment modalities will occur every 28 days for a total of 12 injections (or sham injections). Subjects assigned to receive sham injections will be treated in the same manner as those assigned to the other two treatment arms, except that the hub of an empty syringe (without a needle) is placed against the eye. For the subjects receiving the CLG561 + LFG316 combination, the drugs are mixed extemporaneously and then injected in a single administration.

[figure not shown]
Both eyes must have GA. Only one eye MUST meet the other inclusion/exclusion criteria to be eligible for study participation. Randomization is 1:1:1 (CLG561: CLG561 + LFG316: Sham Injection) and assigned by the IRT.

The study consists of up to 30-Day screening period, an approximate 336-Day treatment period (12 IVT injections occurring approximately every 28 days), and a follow up period consisting of two follow up visits occurring 4 and 16 weeks after the last administered injection.

If a subject prematurely exits the study, then he/she must return to the clinical site approximately 4 weeks after their last injection (or the earliest possible date after 4 weeks) for the EOS evaluation. In this case, all assessments must be completed at the EOS visit.

The following will be masked to treatment assignment:

- Subjects
- Visual acuity assessor at the study site
- Technicians obtaining images at the study site

Figure 3-1 Study design

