3.3 Rationale of dose/regimen and duration of treatment

Rationale for treatment arms

Since GA is a slowly progressive disease, prolonged treatment and observation are required to detect any potential clinical efficacy with CLG561 as a monotherapy or combination of both CLG561 and LFG316. The every 28 day injection frequency is similar to the standard dosing frequency deployed in the LFG316 monotherapy study and in other GA studies conducted with anti-complement agents [the MAHALO trial by Roche testing every 4 week injection of lampalizumab (anti-factor D Fab)].

Based on power calculations, a 12-month treatment period is adequate to measure a clinically meaningful effect. This period of observation depends on available technology, which is currently FAF with semi-automated area quantification using RegionFinder software (Heidelberg Engineering).

Injection of the maximum deliverable concentration of CLG561 (10 mg) is supported by the 26-week IVT toxicity studies in cynomolgus monkeys. Injection of the maximum deliverable concentration of LFG316 (10 mg) is supported by the 26 week IVT toxicity studies in cynomolgus monkeys (605210) in accordance with ICHS6 (R1). The injection of 5 mg CLG561 and 5 mg LFG316 is supported by the 3 month intravitreal CLG561/LFG316 combination toxicology study in cynomolgus monkeys.

As there are no animal models of GA available, the dose-response relationship is unknown for CLG561 or its combination with LFG316. Thus it is proposed to test the highest safe dose of CLG561 (10 mg) as monotherapy. Further monotherapy dose ranging will take place in phase IIb/phase III studies. The combination of 5 mg of each molecule in 100 µL is the maximum feasible volume that can be safely delivered into the vitreous. The combination of CLG561 and LFG316 has shown synergistic efficacy *in vitro* inhibition of complement activation, and in an in vivo murine in vivo model of complement-dependent ocular inflammation. Thus, it is expected that the combination of CLG561 and LFG316 will have superior efficacy in GA as compared to monotherapy.

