11.1 Analysis sets

The final subject evaluability will be determined prior to locking the database.

The full analysis set will be used for assessment of efficacy and the data from both the study eye and fellow eye (fellow eye as reference for the within subject comparison) will be used for analysis. The full analysis set will include all subjects who receive any study treatment and have at least one follow-up visit with an assessment of the GA lesion size. The full analysis set will use the treatment as randomized.

The per-protocol (PP) set will be used for assessment of efficacy and the data from both the study eye and fellow eye will be used for analysis. The PP set will be comprised of all full analysis set subjects who have no critical protocol deviations, and have a valid assessment of the primary efficacy endpoint (change in geographic atrophy lesion size from baseline to Day 337 as assessed by FAF). Key per protocol criteria are compliance regarding the monthly injection schedule up to Day 337 (not missing greater than 1 in any 6 months period or not missing 2 consecutive doses) and in addition to baseline lesion size assessment the corresponding assessment on Day 337 and/or Day 253. Protocol deviations will be identified and classified before database lock. The PP analysis set will use the treatment as randomized. The PP set is the primary efficacy analysis set.

Novartis

Confidential

Page 81

Amended Protocol Version No. 01 (Clean)

Protocol No. CCLG561X2201A

The safety analysis set will include all subjects that received any study drug.

The PK analysis set will include all subjects with available PK data and no protocol deviations with relevant impact on PK data.

The PD analysis set will include all subjects with available PD data and no protocol deviations with relevant impact on PD data.

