11.4.1 Variable(s)

The primary endpoint of this study is the change in geographic atrophy lesion size [mm^2] in the study eye between Day 337 and Baseline as measured by FAF.

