11.4.4 Supportive analyses

The primary efficacy analysis will be performed using the PP set with treatment as randomized. Sensitivity analysis regarding major protocol deviations will be performed on the primary efficacy endpoint using the full analysis set as randomized. In case of deviations from the treatment allocation as randomized the full analysis set will also be analyzed on an as 'as treated' basis.

An additional sensitivity analysis will be performed assuming linear lesion growth in the study for all treatment for the one year observation period using a Mixed-Effect Model Repeated Measure (MMRM) model with random slopes and including class-variables as specified for the primary analysis.

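### Is 0.67 mm² at Day 337 mislabelled as a 33% reduction, given that the interval is 336 days and the growth assumption is per year?

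*Protocol*

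**What the plan says.** Section 11.6 (Sample size calculation) states the target as a difference of 0.67 mm² in lesion growth to Day 337, "representing a 33% reduction in lesion growth rate, assuming an average natural disease progression of 2.0" mm² per year. The synopsis repeats the sentence. Section 11.4.1 defines the primary endpoint as the change in lesion size "in the study eye between Day 337 and Baseline as measured by FAF".

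Section 3.1 gives the length of treatment as "an approximate 336-Day treatment period (12 IVT injections occurring approximately every 28 days". Baseline is Day 1 in the assessment schedules (Tables 8-1 and 8-2), so Day 337 falls 336 days later.

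Elsewhere the protocol describes the same span in rounder terms:

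- Section 3.3: "Based on power calculations, a 12-month treatment period is adequate to measure a clinically meaningful effect".
- Section 11.4.4, for the random-slopes sensitivity analysis: "assuming linear lesion growth in the study for all treatment for the one year observation period".
- Section 11.1, among the per-protocol criteria: "compliance regarding the monthly injection schedule up to Day 337".

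**The concern.** The sentence appears to divide quantities with different time bases. The numerator, 0.67 mm², is a difference accumulated over 336 days. The denominator, 2.0 mm², is given as a yearly rate. A relative reduction in a growth rate needs the same time unit above and below the line. If a year means a calendar year, about 29 days of growth are counted in the denominator and not in the numerator, and the percentage comes out too small.

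The percentage is the only place where the target is put in relative terms, and Section 1.1 quotes results for another complement inhibitor in the same terms (20.4% overall, 42% in a genetic subgroup). A reader comparing trials, or planning the next one, might take 33% at face value. Pressed further, a true 33% reduction in a calendar-year rate of 2.0 mm² would give a Day 337 difference smaller than 0.67 mm², and the trial might have less than 80% power for it.

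**Working it through.** **Inputs.** From Section 11.6: difference 0.67 mm², standard deviation 1.2 mm², one-sided alpha 0.1, power 80%, 30 evaluable per arm, natural progression 2.0 mm² per year, 20% drop-out or protocol deviation. From Section 3.1 and the assessment schedules: Day 1 to Day 337 = 12 × 28 = 336 days, with a visit window of ±5 days at Day 337.

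**1. The plan's own sample size.** Normal approximation: n per arm = 2 × (1.2816 + 0.8416)² × (1.2/0.67)² = 2 × 4.508 × 3.208 = 28.9, so 29. At n = 30 the standard error of the difference is 1.2 × √(2/30) = 0.310 and the noncentrality is 0.67/0.310 = 2.16. Power by noncentral t with 58 degrees of freedom is 80.7%. Inflation for 20% loss: 30/0.8 = 37.5, so 38 per arm and 114 in total. All of this agrees with the protocol, and neither 33% nor 2.0 mm² enters any of it.

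**2. The plan's own percentage.** 0.67/2.0 = 33.5%, stated as 33%. In reverse, 2.0/3 = 0.667, which rounds to 0.67. The target is therefore one third of 2.0, with 2.0 used as the sham growth to Day 337.

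**3. Strict calendar-year reading, linear growth.** Expected sham growth by Day 337 = 2.0 × 336/365.25 = 1.84 mm². Then 0.67/1.84 = 36.4%. Annualising the numerator gives the same result: 0.67 × 365.25/336 = 0.728 mm² per year, and 0.728/2.0 = 36.4%. The difference from step 2 is the growth over 365.25 − 336 = 29.25 days: 2.0 × 29.25/365.25 = 0.16 mm². Over the visit window (331 to 341 days) the percentage runs from 37.0% to 35.9%, so the window does not bring it back to 33%.

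**4. Power for a true 33% reduction on the calendar-year reading.** The difference would be 0.33 × 1.84 = 0.607 mm².

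| Assumption on the standard deviation | SD (mm²) | Power at 30 per arm |
|---|---|---|
| 1.2 applies at Day 337, as the sentence reads | 1.2 | 74.7% |
| 1.2 is annual and scales with time like the mean (1.2 × 336/365.25) | 1.104 | 79.8% |

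**5. Reading in which 2.0 mm² is growth to Day 337.** The reduction is 33.5% and power for it is 80.7%, as in steps 1 and 2.

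**6. Which reading the text supports.** Section 3.3 ties the power calculations to a 12-month treatment period, Section 11.4.4 calls the observation period one year, and Section 11.1 calls the 28-day schedule monthly. The protocol equates twelve 28-day intervals with a year throughout. With the one-third relation in step 2, this favours the reading in step 5. The calendar-year condition has to be brought in from outside.

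**The case for a change.** The strongest case for a change is that mm² per year is a rate, that a year ordinarily means a calendar year, and that the protocol nowhere defines it as 336 days. On that footing 36.4% written as 33% is not rounding, whereas 33.5% written as 33% is. Either the percentage or the unit is loose, and correcting it would take one phrase in two places. If the standard deviation of 1.2 mm² is taken to apply at Day 337, the power for a literal 33% reduction in the yearly rate drops to about 75%.

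The arithmetic stands, and so does the remark that the wording is loose. The conclusion that the figure is wrong does not. It needs a definition of year that the protocol's own usage does not support. Relabelling the target as 36% of 1.84 mm² would also bring in two figures the protocol never uses, in place of an evident target of one third.

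The loss of power does not follow either. The trial is powered for 0.67 mm², not for one third of 1.84 mm². The 75% also requires the mean to scale with time while the standard deviation does not; if both scale, power is about 80%.

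**Conclusion.** No change follows. The 33% is consistent with the protocol's habit of treating 336 days as a year. On a strict calendar-year reading it would be about 36%, assuming linear growth, which is also what the sensitivity analysis in Section 11.4.4 assumes. The discrepancy is about 3 percentage points in a parenthetical description of an absolute difference that is itself correctly stated and correctly powered.

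Nothing the trial does or can conclude depends on that description. Section 11.4.2 tests each active arm against sham with a null boundary of 0 mm². The sample size, alpha and analysis model make no use of the percentage, and no decision rule visible in the protocol refers to it. Someone who wants the relative effect on another time scale has 0.67 mm², 2.0 mm² and Day 337 in the same sentence and can convert it. Stating the growth assumption as growth to Day 337 would read more cleanly, but that is an optional matter of wording with no statistical gain.

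This rests on reading 2.0 mm² as growth over the study year. That is inferred from Sections 3.3, 11.1 and 11.4.4 and from 0.67 being one third of 2.0; the protocol does not say it outright. Even if the inference were wrong, only the label would change.
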